Participants. Participants are mother-child dyads composing of a mother caregiver and a child who is aged 6-12 years (primary school student) and fulfils the diagnostic criteria for *mild* grade to moderate grade ID (based on the age-relevant IQ test assessments administered by a qualified professional). In the judgment of health/school professional staff, the child is capable of responding to assessments and participating in group activities. The dyads are able and willing to give consent for participation in the study (guardian's assent consent will be arranged for the participating children, while written consent will obtained from the adult mothers). Dyads are excluded if: (i) the dyad is currently participating in any other behavioral or pharmacological trial, and/or (ii) either member of the dyads have other contraindications or severe comorbidities that may impair their full participation (e.g. severe physical disabilities).

Recruitment. The recruitment will be facilitated by our collaborative partners in the community (including SEN schools, and community-based units that serve families of children with ID), as well as referral from medical and mental health professionals working in the field of education, paediatric psychiatry, clinical psychology, and social work. The promotion materials will be hosted on the website/social media of the Department of Social Work and Social Administration and Centre on Behavioural Health of The University of Hong Kong. Screening for eligibility will be conducted by the researcher or referral professionals who have attended briefing sessions offered by the research team.

Sample Size: We expected a moderate effect size of 0.5 for the primary outcomes based on a local study [57]. Using power analysis software Gpower 3.1, assuming an attrition rate of 20%, a total sample size of 154 participants (i.e. 77 each arm) will provide 80% statistical power to detect an effect size of 0.5 in the 2-arm RCT with 4 measurement time points at 5% level of significance. For the qualitative data collection, a random subsample of 30 participating mothers will be invited to join individual, in-depth interviews at post-intervention (T₁) and 6-month follow-up (T₂). Based on various guidelines for mixed methods study design, a sample of 25 participants would suffice data saturation. If data saturation is not reached, more participants will be recruited into the study until no more new findings emerge [34].

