In-depth Interviews: 30 participating mothers will be invited to attend two individual, in-depth interveiws at post-intervention (T₁) and 6-month follow-up (T₃) respectively. The first interview focuses on the immediate post-intervention changes percieved by the mothers upon program completion, while the second interview focuses on the sustainability of these changes at 6-month follow-up and explores additional changes that were observed between the follow-up windows. The interviews will be conducted by member of the research team (who are familiar with mixed-methods study design, in-depth interview), assisted by a research assistant, using an interview guide [57]. **Appendix D** shows the sample interview guide and its potential probes.

Data Analysis: Analyses of the outcomes will be performed according to standard intent-to-treat principle to address the effects of crossover and dropout. Missing data for the participants who drop out of the study at follow-up assessments will be handled using the full information maximum likelihood method. This method has been shown to produce unbiased estimates for clinical trials with missing data [58].

[figure not shown]
- 1. Effectiveness of Dyadic EXAT group (Hypothesis 1 3). Descriptive statistics will be used to summarize the socio-demographic characteristics of the participants at all time points. Primary analysis of treatment outcomes will be conducted using mixed-effects regression models. Mixed-effects models analyze the repeated measurements between groups to obtain the time effect, group effect, and group*time effect. The analysis will adopt the intention-to-treat principle to account for the missing data. Missing data for participants' dropout will be handled using full information maximum likelihood method [58]. Effect size of the intervention will be evaluated using Cohen d [59], with 0.2, 0.5, and 0.8 denoting cut-off of small, moderate, and large magnitudes. Demographic and clinical variables will be controlled in the analysis. All statistical tests will be two tailed and statistical significance will be set at 0.05 using Mplus 8.3.

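### Is the 80% power claim for 154 dyads wrong because attrition was allowed for by multiplying by 1.2 instead of dividing by 0.8?

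*Combined protocol and SAP*

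**What the plan says.** Under Research Plan and Methodology, the Sample Size paragraph names G*Power 3.1 as the software. Its power claim reads: "assuming an attrition rate of 20%, a total sample size of 154 participants (i.e. 77 each arm) will provide 80% statistical power". The target of that calculation is worded as follows: "detect an effect size of 0.5 in the 2-arm RCT with 4 measurement time points at 5% level of significance". The effect size is introduced with "We expected a moderate effect size of 0.5 for the primary outcomes based on a local study [57", and that number in the reference list is an interview protocol. The In-depth Interviews paragraph cites the same number where it fits: "using an interview guide [57".

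The other relevant settings are in the Data Analysis section. Tests are two-sided: "All statistical tests will be two tailed and statistical significance will be set at 0.05 using Mplus 8.3". The effect-size metric is given there too: "Effect size of the intervention will be evaluated using Cohen d [59], with 0.2, 0.5, and 0.8 denoting cut-off of small, moderate". The primary analysis is a mixed-effects model: "Mixed-effects models analyze the repeated measurements between groups to obtain the time effect, group effect, and group*time effect". Missing data from dropouts "will be handled using full information maximum likelihood method [58".

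**The concern.** Anyone checking the figure will start with a two-sample t-test at d = 0.5, two-sided 5% and 80% power. It needs 64 per arm, and adding 20% gives exactly 77 per arm and 154 in total. That looks like a familiar slip: to keep n completers after a 20% loss one divides by 0.8, and multiplying by 1.2 falls short. If so, the trial would be 6 dyads short of what its own assumptions require, and the 80% would be overstated.

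The paragraph also withholds what is needed to confirm or dismiss this. It does not say which G*Power test was run, which contrast was powered, what within-person correlation was assumed, or how many completers were required. The source given for the 0.5 cannot supply an effect size. At stake would be the credibility of the stated power for the primary outcomes.

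**Working it through.** **Inputs from the document.** Effect size 0.5, 5% level, 80% power, 20% attrition, 154 dyads (77 per arm), two arms and four visits (Sample Size); 1:1 allocation (Group Allocation); two-sided tests and Cohen d (Data Analysis). The within-person correlation r is not given, so every value of r below is an assumption.

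**1. Reproducing 154 by the t-test route.** With n per arm, the noncentrality is d x sqrt(n/2) on 2n - 2 degrees of freedom.

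- n = 63: power 79.5%.
- n = 64: power 80.1%. So 64 per arm, 128 in total.
- 64 x 1.2 = 76.8, rounded up to 77; 128 x 1.2 = 153.6, rounded up to 154. Both printed figures match.

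**2. The attrition step on that route.**

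- Needed to keep 128 completers: 128/(1 - 0.20) = 160, which is 6 more than 154.
- Completers left from 154: 154 x 0.8 = 123.2, or 61.6 per arm; power 78.6%.
- Shortfall: 80.0 - 78.6 = 1.4 percentage points.
- Attrition at which 128 remain: 1 - 128/154 = 16.9%.
- By normal approximation: 63 per arm, 126/0.8 = 157.5, so 158 dyads; power at 61.6 per arm 79.2%.

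**3. Is that the only route to 154?** No. Take the group-by-time F test with two groups and four visits, assuming sphericity: noncentrality = f² x N x 4/(1 - r), with 3 and 3(N - 2) degrees of freedom.

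- Differences of 0, 0.5, 0.5, 0.5 across T0 to T3: mean 0.375, sum of squared deviations 0.1875, f² = 0.1875/16 = 0.0117, f = 0.108. At r = 0.476 the noncentrality is 0.0117 x 123.2 x 4/0.524 = 11.0, and 123.2 completers give 80% power. Dividing by 0.8 returns 154.
- Linear rise to 0.5 at T3: sum of squared deviations 0.1389, f² = 0.0087, f = 0.093. 123.2 completers give 80% at r = 0.612.

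These values of r were solved for, so they do not show that the sponsor used them. But 128 and 1.2 were solved for in the same way. Against this, the conventional medium effect f = 0.25 with r = 0.5 does not lead to 154: it needs 24 completers for the interaction or 82 for the between-group test.

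**4. Power of the kind of analysis planned, at 123.2 completers.**

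| Contrast | r = 0.3 | r = 0.5 | r = 0.7 |
|---|---|---|---|
| Group-by-time, d = 0.5 at T1, T2 and T3 | 66% | 82% | 97% |
| Group-by-time, linear rise to d = 0.5 at T3 | 52% | 68% | 90% |
| Group difference at one visit, adjusted for baseline | 82% | 89% | 97% |
| Mean of three post-baseline visits, adjusted for baseline | 98.5% | 98.9% | 99.9% |

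The last two rows use the two-sample formula with d divided by sqrt(v), where v = 1 - r² for one visit and v = (1 + 2r)/3 - r² for the mean of three. All rows drop every dropout, whereas full information maximum likelihood keeps their partial data.

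**The case for a change.** The strongest case for acting has three parts.

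First, 128 x 1.2 fits both 77 and 154 using round inputs, while the repeated-measures routes need particular correlations. That makes the t-test origin the more natural guess, and on it the stated power is wrong in a known direction. The guess is reasonable, but it is still a guess. It discards the one design feature the paragraph reports, the four visits, and it leads only to 78.6% against 80%.

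Second, whichever origin is right, the correlation and the pattern of effect over time decide whether 80% holds for the group-by-time test, and neither is stated. This part stands: the paragraph is thinner than good practice, and a reader cannot verify the figure. It is an omission in the reporting, though, and it does not show that the figure is wrong.

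Third, the citation for the effect size is plainly misnumbered. That also stands. It is a clerical slip: the same number is used correctly for the interview guide, and no analysis depends on it.

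Rewriting the power statement would gain little. Printing 78.6% would describe a completers-only comparison at a single visit, which the Data Analysis section does not plan. Confirming the true origin needs the sponsor's G*Power inputs, which the document does not contain, and might leave the 80% exactly as it is.

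**Conclusion.** No change to the plan follows. The arithmetic behind the suspicion is correct: 64 per arm, 153.6 after multiplying by 1.2, 160 after dividing by 0.8, and 78.6% at 154. It applies only if a two-sample t-test multiplied by 1.2 was used, and the document does not say so. On that assumption the overstatement is 1.4 percentage points (0.8 by normal approximation) and 6 dyads, and 80% still holds with attrition up to 16.9%.

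For the planned mixed model, power cannot be fixed from the document. At 154 dyads with 20% loss it runs from about 52% to above 99% over the contrasts and assumed correlations shown, which lies on both sides of the stated 80%. Underpowering is therefore not shown.

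What is left is missing detail in one paragraph and a wrong reference number. Neither affects the number randomized, the analysis, or how the results would be read.

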Acquiring New Ways of Relating. The dyadic EXAT emphasizes the process of co-creation and exploration with arts; which encourages joint looking and shared sensory experiences between the mother and child. This will prompt the dyads to try out new strategies to communicate and relate to each other [2], facilitate better communication, and help secure their attachment [24]. Such exploration will also allow children more room to express or in charge of this new dynamic; open new ways for the mothers to understand, appreciate, and interact with their children [27]; benefit the relationship; enhance parental sensitivity; and facilitate the improvements of caregiving burden and well-being for the dyads [23].

Soliciting Social Support Within and Between the Families. Dyadic group intervention allows social support to synergistically emerge between the family dyads; whereas experiences of one family unit could provide the avenue for other families to model alternative communication patterns [26, 27]. When the group uses arts to share what they normally cannot verbalize, they open up possibilities for unexpected common themes for discussion and exploration [27]. The dyadic group format also allows the mother to connect more with the program, display attention, kindness, and appreciation of the child, rather than only learn practical skills for their children or resolve their own emotional issues [26].

Although evidence are accumulating on the use of arts-based elements to help families with children having disabilities to cope, existing evidence is plagued by: (i) small sample or not homogenous sample of children with ID; (ii) not having children in the intervention, (iii) no exploration on children's emotional expression and mood in outcomes; (vi) interventions with single art modality; (v) without post-intervention data collection time points. To address the above limitations and knowledge gaps, this study may generate rigorous multi-dimensional research evidence to support the use of dyadic EXAT which puts equal emphasis on the experiences and interaction of the mothers and children with ID. The study will bridge both the knowledge gap on the application of dyadic EXAT and service gap in supportive care for families with children having ID or other special needs (SEN) locally and internationally.

Work Done by the Team

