Group Allocation. Eligible family dyads will be randomly assigned into one of the two study conditions on a 1:1 basis using a randomization table and a computer-assisted random number

generator. The allocation list will be produced by an independent researcher and concealed from other researchers and participants until assignment.

(a) *The Dyadic Expressive Arts Group Therapy:* The 8-session intervention group (weekly session, 90 minutes each, with 3-4 dyads in 1 group) delivered will be by a registered Expressive Arts Therapist or an expressive arts therapy trainee, or a mental health professional trained in expressive arts intervention (under supervision). Each session consists of 5 basic processes in EXAT: check-in, warm-up, core art making, sharing, and closure [35]; and focuses on a specific theme related to parent-child relationship: communication, relationship, expression, empathy, interaction, love, gratitude, and connection. The program has been developed and adopted for people with ID and mothers of children having special needs and disabilities [1, 2, 36], and has been refined to integrate the cultural-relevant components (e.g. Chinese festivals, Chinese arts and music, etc.) and parent-child interaction skills and elements [2, 3]. The program has been used by the team in previous studies and community workshops [37-40]. **Appendix C** summarizes the structure of the program.

(b) *The Treatment-as-usual Waitlist Control Group*: The control group will continue with routine healthcare and social services and will be invited to participate in a similar intervention group program upon completion of the 8-month study period.

Treatment fidelity: Group facilitators participating in the intervention delivery will receive a training session covering the details of the protocol and safety precaution. Treatment fidelity will be assessed by the PI in the form of on-site or video-reviewing supervisions, preferably during the 3rd or 4th session on the condition that written consents are provided by the participants. The facilitators will receive off-site supervision provided by the PI. The assessment will be conducted using a pre-constructed observation checklist outlining the program pedagogy and the expected goals of the sessions.

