- 8. *Emotional expression*. The Face Stimulus Assessment [51] is an arts-based projective assessment which is a viable means of extracting psychological information including emotional expressions for individuals with communication difficulties, including ID [52]. The assessment contains a series of three A4-size stimulus drawing templates: the first is a pre-drawn face, the second is a face outline, and the third is a blank sheet of paper. Participants will be asked to use the markers provided on the templates individually. The FSA will be administered in small groups and assessed through a quantitative and qualitative approach following guidelines from the FSA E-Packet and Rating Manual (2nd ed.) [51, 53]. The artworks will also be digitally scanned to analyze the pattern of color usage [1]. This assessment will be conducted by a trained Expressive Arts Therapist, a EXAT Trainee under supervision, or a trained research staff.
- 9. Behavioral and emotional problems. The 113-item Child Behavior Checklist (Teachers' Report Form) measures behavioral and emotional behaviors related to child functioning and problem behaviors observed by the teachers/professionals [54]. The Chinese version is widely adopted in Hong Kong with established local norms [55]. School teachers or social workers of the participating children will be invited to fill in the checklist and indicate the degree or frequency of the behaviors described in the checklist on a scale of 0 (not true), 1 (somewhat or sometimes true), or 2 (very true or often true). The checklist yields three composite scores on externalizing, internalizing, and total behavioral problems, and eight syndromes of withdrawn, somatic complaints, anxious/depressed, thought problems, social problems, attention problems, deliquent behaviors, and aggressive beahvior with higher scores indicating greater manifestations of the described behavior problems in the area [56].

Other variables

10. *Demographics*: Participant profile including age, gender, education level, income, employment status, religiosity, marital status, and family composition will be recorded. Clinical information (time since onset/ diagnosis, medical treatment record, psychiatric

history, comorbidity (physical disabilities, hypertension, diabetes mellitus, or other cognitive disturbance) and history of rehabilitation service utilization of the parents and children will be documented.

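### The plan gives no therapy-group effect for dyads treated in groups of 3-4, so standard errors are too small if outcomes correlate within groups

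*Combined protocol and SAP*

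**What the plan says.** Under Group Allocation, item (a), dyads are randomised individually and the EXAT arm is treated in a "weekly session, 90 minutes each, with 3-4 dyads in 1 group" format over eight sessions. The facilitator may be a registered therapist, a trainee or another trained professional. Item (b) leaves the controls on usual services; they "will be invited to participate in a similar intervention group program upon completion of the 8-month study period".

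The background section on social support within and between families says "Dyadic group intervention allows social support to synergistically emerge between the family dyads" and adds that "experiences of one family unit could provide the avenue for other families to model alternative communication patterns". Appendix C lists mutual support in the group among the purposes of a session.

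Data Analysis, item 1, describes the primary model as follows: "Mixed-effects models analyze the repeated measurements between groups to obtain the time effect, group effect, and group*time effect". The word group there means trial arm. Demographic and clinical covariates are added. No therapy-group or facilitator effect and no cluster-robust variance appears anywhere.

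The Sample Size paragraph claims "80% statistical power to detect an effect size of 0.5 in the 2-arm RCT with 4 measurement time points", with 20% attrition and 77 dyads per arm. It gives no ICC, design effect or within-dyad correlation.

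**The concern.** Dyads in one therapy group share a facilitator, eight sessions and each other's company. If groups differ in how well they work, dyads from the same group resemble one another after baseline, and 77 EXAT dyads carry less information than 77 independent ones. A repeated-measures mixed model handles correlation within a dyad over time. It does not handle correlation between dyads unless a term is added for it.

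Therapy-group clustering sits in one arm only, so the design is partially nested. Leaving it out makes the standard error of the arm comparison too small, the confidence interval too narrow and the type I error too high, and this falls on the primary effectiveness tests. If group membership is not kept as an analysis variable, nobody can later estimate the ICC or show that a result survives allowing for it.

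**Working it through.** **Inputs from the documents.** 77 dyads per arm, 1:1; groups of 3-4 in the EXAT arm only; effect size 0.5; 20% attrition; two-sided 5%; 80% power.

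**Assumptions.** The documents give no ICC, so 0.01 to 0.20 is used. Dropout is random and thins the groups. Outcomes have unit variance.

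**Reproducing 154.** A two-sample t-test for d = 0.5 with 80% power needs 64 per arm. 64 × 1.2 = 76.8, rounded up to 77, so 154 in total. Repeated-measures calculations (f = 0.25, four times, assumed correlation 0.5), inflated for dropout, give about 98-103 for the between-arm test and about 29-30 for the interaction. The match suggests that 154 rests on independent dyads. It does not prove it, since the paragraph mentions four time points.

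**Number of groups.** At most 4 per group: 77/4 rounds up to 20 (17 of 4 and 3 of 3). At least 3 per group: 77/3 rounds down to 25 (23 of 3 and 2 of 4).

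**One post-baseline time.** For group size m, a retained dyad has on average k = 0.8(m − 1) partners left, so k = 1.6 (m = 3) or 2.4 (m = 4). The EXAT-arm design effect is DE = 1 + k × ICC. The control arm has DE = 1, so the true-to-assumed variance ratio is R = (1 + DE)/2. Type I error is 2 × [1 − Φ(1.96/√R)].

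Example, m = 4 and ICC 0.20: DE = 1 + 2.4 × 0.20 = 1.48; R = 1.24; √R = 1.114; type I error 7.8%.

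Power uses 77 × 0.8 = 61.6 dyads per arm on a t-test basis, with the effect divided by √R.

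| ICC (assumed) | True SE above unclustered SE | Type I error | Power at d = 0.5 |
|---|---|---|---|
| 0 | 0 | 5.0% | 78.6% |
| 0.01 | 0.4-0.6% | 5.1% | 78.1-78.3% |
| 0.05 | 2-3% | 5.5-5.7% | 76.2-77.0% |
| 0.10 | 4-6% | 5.9-6.4% | 73.9-75.5% |
| 0.20 | 8-11% | 6.9-7.8% | 69.6-72.4% |

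The 78.6% in the first row comes from multiplying by 1.2 instead of dividing by 0.8. It has nothing to do with clustering.

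**Average of T1-T3 minus T0.** With within-dyad correlation ρ, the variance per dyad is v = (1 + 2ρ)/3 + 1 − 2ρ, which is 0.667 at ρ = 0.5 and 0.933 at ρ = 0.3. Then SE² = (2v + k × ICC × f)/61.6. Here f = 1 if the group effect persists in full, and f = [(1 + 0.5 + 0.25)/3]² = 0.34 if it halves at each follow-up.

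Type I error at ρ = 0.5:

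| ICC (assumed) | Persistent | Halving |
|---|---|---|
| 0.01 | 5.1-5.2% | 5.1% |
| 0.05 | 5.7-6.1% | 5.2-5.4% |
| 0.10 | 6.4-7.1% | 5.5-5.7% |
| 0.20 | 7.8-9.3% | 6.0-6.4% |

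Power for this contrast, from the same formula with a persistent group effect:

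| ICC (assumed) | ρ = 0.5 | ρ = 0.3 |
|---|---|---|
| 0 | 92.5% | 81.9% |
| 0.05 | 90.2-91.0% | 79.5-80.3% |
| 0.10 | 87.9-89.5% | 77.1-78.7% |
| 0.20 | 83.0-86.3% | 72.6-75.6% |

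**Simulation** (77 per arm, both group layouts, 20% random dropout, 40,000 trials per setting). The unclustered test at one time gave 5.5-5.7%, 5.9-6.4% and 7.0-7.7% at ICC 0.05, 0.10 and 0.20, in line with the formula. Over ICC 0 to 0.20, type I error for the candidate remedies was:

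| Method | Type I error |
|---|---|
| Partially nested model, REML, Satterthwaite degrees of freedom | 4.4-5.0% |
| Same model with 1.96 | 4.8-5.6% |
| Corrected cluster-robust variance, Satterthwaite degrees of freedom | 4.8-5.3% |
| Uncorrected cluster-robust variance with 1.96 | 5.7-6.2% |

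**The case against.** **The effect is small.** At an ICC of 0.05 or below, type I error at one time point stays at or under 5.7%. The 9.3% maximum needs ICC 0.20, groups of 4, full persistence, correlation 0.5 and an averaged contrast that the plan does not name as its test. This stands, and it limits the severity.

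**Mutual support is not the same as correlation.** Support that helped every group equally would raise the mean and create no ICC. That is right, and the background text says only that influence may arise. But equal benefit in every group cannot be assumed when peers and facilitators differ. The manual, training, supervision and fidelity checklist may limit facilitator differences; they do not remove peer influence.

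**The plan is underspecified, not wrong.** The random-effects structure is not spelled out, and a mixed model could hold a therapy-group term. That is fair, but an analyst following the text would have no reason to add one.

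**The plan uses maximum likelihood in Mplus 8.3, not REML.** In one small simulation (6,000 trials per setting), a partially nested maximum likelihood model with 1.96 gave about 5.3% at ICC 0.05 and 5.8-6.2% at 0.10, so the gain at low ICC is slight. A separate check at ICC 0.20 found that 7.4-8.2% fell to 5.9-6.1% with 1.96 and to 5.4-5.5% with small-sample degrees of freedom. Most of the inflation at the higher ICC goes, but under maximum likelihood the degrees of freedom matter.

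**No power loss is shown.** This stands. Power depends on the ICC and the within-dyad correlation, and the plan states neither.

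**Conclusion.** The concern holds. The plan provides for group delivery in one arm, describes influence between families as a route of effect, and states neither a therapy-group term nor an ICC. Whenever the ICC is positive, the analysis as described understates the standard error of the arm comparison.

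The size is conditional on an ICC that the documents do not give. At one time point the inflation is under 1 percentage point for ICC up to 0.05 and about 1 to 3 points for 0.10 to 0.20. It can be larger for an average over follow-up if group effects persist. No shortfall in power is established. The point should be fixed because the error runs in the anti-conservative direction on primary outcomes and the correction is cheap, not because the likely distortion is large.

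**What to change.** 1. Record therapy-group, facilitator and recruitment-site identifiers for every dyad.
2. In the primary model, add a therapy-group random effect on post-baseline outcomes in the EXAT arm only (a partially nested model), with small-sample degrees of freedom. The alternative is a small-sample-corrected cluster-robust variance with each control dyad as its own cluster. Choose one in advance.
3. Confirm that Mplus 8.3 provides the chosen correction, or name software that does.
4. State how dyads are put into therapy groups. Recruitment runs through partners, "including SEN schools, and community-based units that serve families of children with ID", and for the behaviour checklist "School teachers or social workers of the participating children will be invited to fill in the checklist". Site or rater correlation is a separate matter that can occur in both arms. If groups are formed by school or centre, include recruitment site in both arms so that site variance is not mixed with therapy-group variance. In a simulation assuming 8 sites, groups formed within site, site ICC 0.10 and therapy-group ICC 0 to 0.10, the corrected robust variance gave type I error of 3.8-4.5% and power of 71.1-75.5% without site terms, against 4.8-5.3% and 74.6-79.2% with them. At site ICC 0.05, omitting site mattered little.
5. Report the estimated ICC for each primary outcome, and restate the power of 154 dyads over a range of ICC and within-dyad correlation.

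The cost is SAP wording, one random effect (plus a site term if groups follow sites), three identifiers already known from delivery and recruitment, and a software check or change. Confidence intervals widen slightly. If the ICC is truly zero, the mixed model is slightly conservative (type I error 4.5-4.6%) and loses about 2 points of power; the corrected robust variance loses under 1 point. The restated power may look less favourable. No extra dyads are needed.
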